Participants will be assisted with downloading the appropriate app, provided instructions on how to use the app (*iCaminemos Juntas!* or *World Walking*), and encouraged to use the app daily.

6-week interim assessment: Participants will complete interim assessments of initial changes. An invitation email and text messages containing a link to the interim surveys along with their unique password (PIN number) will be sent. Participants will complete the web-based surveys using either their computer or smartphone; no in-person meeting will be required. Participants who do not complete the surveys within 3 days will receive an email and text reminder (and 3 more reminders at 3-day intervals if still not completing it).

12-week post-test assessment: Participants will complete an in-person post-test assessment. They will meet individually with a study staff to complete the online surveys on a study tablet and a brief post-test interview.

3C.6.2. Outcomes: Baseline, Interim, and Post-test Measures. The baseline, 6-week interim, and 12-week post-test surveys will use validated scales to measure the primary outcome – physical activity - and secondary outcomes of social and environmental support and quality of life (QOL). Surveys should take 30-45 minutes to complete. See **Table 4** for schedule of measurements.

TABLE 4: Schedule of Measurements

Assessment	Screening	Pre-test/Baseline	Week 6	Week 12/Post-test
Inclusion Screener	X			
Physical Activity		X	X	X
Social & Environmental Support		X	X	X
Quality of Life (QOL)		X	X	X
Usage Data (iCaminemos Juntas! app only)			X	X
System Usability Scale (iCaminemos Juntas! app only)				X

Physical Activity:

The Community Healthy Activities Model Program for Seniors (CHAMPS¹⁶⁰) is a 41-item PA questionnaire that measures self-reported minutes-per-week of PA calculated as total weekly caloric expenditure in all PA. It was developed for underactive populations and validated among older adults.¹⁶⁰ However, CHAMPS has been used with younger and racially/ethnically diverse populations; it is sensitive to change specifically in Latino and other populations including ones younger than senior age.¹⁶⁴⁻¹⁶⁷ The CHAMPS asks about activities undertaken for exercise, daily activities that are physical in nature, and physically active recreational activities during “a typical week in the past 4 weeks.” CHAMPS has strong psychometric properties,^{160,168} including validation in Spanish and sensitivity to change.¹⁶⁹⁻¹⁷¹

Social and Environment Support:

*Neighborhood Environment Walkability Scale-Abbreviated (NEWS-A)*¹⁷²: The 54-item NEWS-A assesses residents' perception of neighborhood design features related to PA, including residential density, land use mix, street connectivity, infrastructure for walking/cycling, neighborhood aesthetics, traffic and crime safety, and neighborhood satisfaction. It is a validated measure of neighborhood walkability with adequate levels of factorial and criterion validity,^{172,173} and has been used with Latino populations.¹⁷⁴

*Social Support for Exercise Survey*¹⁷⁵: This 13-item self-report measure assesses perceived receipt of social support for exercise, i.e., how often their friends or family members (separately rated) encouraged their exercise behaviors during the previous 3 month. It yields two separate scores for friends- and family-encouragement (score range=13 to 65 for family and friends with higher scores reflecting higher encouragement). This measure has good psychometric properties and has been used with Latino populations.¹⁷⁶⁻¹⁷⁸

Quality of Life (QOL):¹⁷⁹ The 12-Item Short Form Health Survey (SF-12) measures functional health and well-being (i.e., health-related quality of life; HRQOL). The SF-12, an abbreviated version of the SF-36, covers the same 8 health domains, and produces a physical and mental component summary score (PCS; MCS). The SF-12 is often used in population studies including those focused on Latinos¹⁸⁰⁻¹⁸² and has been found to be a reliable and valid measure of HRQOL.^{179,183} Higher scores indicate better physical and emotional well-being.¹⁸³

*Environmental Supports for Physical Activity Questionnaire – Social and Physical Environment Survey*¹⁸⁴: This questionnaire assesses neighborhood physical and social environments, i.e., neighborhood safety, access to recreation and shopping destinations, and conditions of neighborhood and facilities. It was tested for reliability and validity among 1200 adults, and has shown good psychometrics properties in other studies.^{173,185-187}

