3C.1. Phase II Project Overview. The Phase II project will be conducted over 24 months. The *iCaminemos Juntas!* app will be fully developed in Months 1-9 and evaluated for disseminability (i.e., can LBS database procedures and LBS functionality from Phase I be translated to a new geographical location) and behavior change (i.e., increased PA) in Months 10-24 among a sample of Latinas aged 18-55 years (upper age limit was increased per Phase I feedback from EAB, CAB, and study participants). *iCaminemos Juntas!* will be a stand-alone app that provides person-specific, location-based feedback to help users connect with Latinas in neighborhood-specific geographic areas to promote increased walking behavior. Using the user-centered design (UCD) approach from Phase I, focus groups and usability testing conducted in Colorado and California

will guide final app development. A comparative-effectiveness trial¹³⁶ will enroll and randomize Latino women in a randomized pretest-posttest controlled design. Participants will be recruited from Denver, CO and San Jose, CA and randomized individually to either the *iCaminemos Juntas!* app (experimental condition) or the *World Walking* app (comparison condition). All participants will use the apps for 12 weeks. The primary outcome will be improvements in physical activity post-treatment. Participants (n=200; n=100 per site) will complete baseline, 6-week, and 12-week assessments.

FIGURE 3: Project Timeline

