Usability outcomes: Field usability testing interviews will be recorded, transcribed, and analyzed using Atlas.ti[®] software. Emerging codes will be assigned to phrases and text passages that categorize views, themes, and opinions. The qualitative analysis will rely on constant comparative analysis (based on grounded theory methodology),¹⁵⁵ and a phenomenological approach.^{156,157} To identify problems that impact $\geq 10\%$ of app users^{158,159} with a 95% chance of detection ($\log(1.95)/\log(1.10)$), 28 usability testers are needed. The SUS measure will serve as the primary usability outcome. Additional usability testing outcomes will include app usage data (e.g., log-ins, walks created, etc.). Frequency of responses and proportions and means will be calculated and compared on demographics, using chi-square, t-tests, and correlations, with 2-tailed p=0.05.

3C.4. Experimental Design (Specific Aim 3). The *iCaminemos Juntas!* app will be evaluated in a randomized two-arm, comparative-effectiveness pre-post design. *iCaminemos Juntas!* will be compared to a free and readily available comparison app (*World Walking*, selected because of its primary focus on walking) over 12 weeks. Individuals will be randomized to one of two experimental conditions, using a customized computer program written by KB's biostatistician, [name]. We will recruit a total of 200 community-dwelling Latinas; 100 from the Denver area and 100 from the San Jose area. The primary outcome is change in PA (as measured by the Community Healthy Activities Model Program for Seniors [CHAMPS]¹⁶⁰) relative to baseline. PA was chosen as the primary outcome because Phase I participants strongly expressed that improving their PA level was the main reason why they would use the app.

FIGURE 5: Phase II Study Design

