3C.5. Target Population. There are two target populations: community-dwelling Latinas in (1) the Denver area and (2) San Jose, CA area. Two locations were chosen because: (1) the Phase I functional prototype was developed and field tested in Denver so testing the fully-developed app in the same location saves costs and allows iterative changes to the app to be made quickly, and (2) testing the fully-developed app in a second, remote location (a) allows the research team to test the fidelity of the LBS-database development protocol in a new location, which provides valuable insight on database development for Phase III, and (b) tests the app with a different demographic makeup of U.S. Latinas.

3C.6. Trial Conduct.

3C.6.1. Recruitment and Visit Procedures.

Recruitment and Screening: Potential study participants will be recruited primarily through mass mailings, newspaper and social media ads, and existing research participant databases. Interested participants will be sent an email describing the study and a link to a screening survey administered on KB's secure server that assesses inclusion and exclusion criteria (see **Table 3**), demographic characteristics, and physical activity readiness measured by the Physical Activity Readiness Questionnaire (PAR-Q).¹⁶¹ Prior to enrollment in exercise RCTs, participants' level of risk regarding their ability to safely participate in and increase their level of PA should be assessed.^{162,163} The PAR-Q is commonly used for this purpose and can identify individuals who can safely participate in PA without obtaining medical clearance.¹⁶³ The online screener will take about 5 minutes. Participants will receive an email to inform them of their eligibility status. Eligible participants will be scheduled for an orientation and baseline assessment visit; a reminder email and text message will be sent 3 days prior to the assessment date (similar reminders will be sent for 6- and 12-week visits).

Orientation and baseline/pre-test assessment: Participants will attend a one-on-one orientation and baseline assessment session. Participants will have the study explained and provide written consent. They will complete five online surveys using a tablet computer, which should take about 45 minutes to complete. After survey completion, participants will be randomized using the software and randomization allocation.

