3C.6.3. *iCaminemos Juntas!* Intervention (n=100). A description of the *iCaminemos Juntas!* app was provided in **Section 3C.4.** Participants will download the app following the procedures outlined in **Section 3C.7.1.** Project staff will provide *iCaminemos Juntas!* users a one-one-orientation to the app and how to use its unique features. Daily alerts and notifications will engage users in daily use of the app and provide up-to-date information on users' progress. Participant responses will also be used to evaluate additional or on-going support of users' needs (e.g., increase/ decrease prompts based on user preferences, tailored messages around a set goal, etc.). To protect privacy and to ensure that the participant is the person completing the app activities, KB will uniquely identify the user's smartphone based off the device's "hardware footprint". The app will upload all app activity data to the KB secured web server database.

3C.6.4. World Walking App Comparison Group (n=100). *World Walking* (www.worldwalking.org) is an app available for free on both iOS and Android platforms.¹⁹⁶ It allows users to track walking steps using the phone's LBS features, display walks on a virtual route, create virtual walking groups (you and other users can have shared goals for walking a certain distance such as walking the Great Wall of China), chat with virtual group members, earn badges for meeting goals, connect to Fitbit, and receive push notifications. There are a number of similarities between the two apps; participants will be able to track their walking, have a reward-based system for meeting goals, map their walks, use Fitbit, and have a social network component. The app encourages social interaction by letting walkers form virtual clubs, working together to meet distance targets.

However, while there are similarities between the two apps, *World Walking* will not allow for real-time, in-person social connection (meeting other women in-person and walking locally), or connection to social media.

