Aim 1 will be assessed by examining the number of connections/matches for walking (creating and/or joining a walk). We believe that at least 70% of the *iCaminemos Juntas!* intervention group will establish at least one connection and participate in at least one walk (e.g., 78% of users in Phase I created at least one walk). The distribution of number of connections and walks completed will be examined. We will test whether there is a difference between the groups in connections that occurred using a chi square test and will further test a single proportion that the *iCaminemos Juntas!* group will have significantly more than 70% active participation as evidenced by making at least 1 connection.

Aim 2 will be evaluated descriptively and via feasibility testing showing that location-based services can be replicated regardless of region.

Aim 3 is critical to product development and will evaluate whether *iCaminemos Juntas!* increases physical activity, social support, and quality of life (QOL) in Latinas. Three hypotheses for the comparative-effectiveness trial will be examined:

H₁: Latinas randomized to the *iCaminemos Juntas!* app will report greater improvements in their physical activity compared to Latinas randomized to the comparison app (*World Walking* app) at 12-weeks post-test.

H₂: Latinas randomized to the *iCaminemos Juntas!* app will report greater increases in their social support for exercise compared to Latinas randomized to the comparison app at 12-weeks post-test.

H₃: Latinas randomized to the *iCaminemos Juntas!* app will report greater improvements in their quality of life (QOL) compared to Latinas randomized to the comparison app at 12-weeks post-test.

Additional secondary analyses will (1) evaluate immediate changes in the PA, social and environmental support, and QOL measures at 6 weeks; (2) assess mediators at 6-weeks for a mediational analysis on 12-week outcomes; and (3) evaluate app usage data (e.g., number of log-ins, number of “check-ins”, EMA responses for likability and satisfaction with the app).

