Tests will be performed as per the design using simple t-tests followed by analysis of covariance to assess the outcome results adjusted for baseline (rather than change from baseline). Multivariate analyses will be conducted to assess the simultaneous direction of changes in the components between the treatment arms. We will test the outcomes simultaneously and examine the correlation amongst them within treatment arms. Hotelling’s T² will be used to test the overall mean vector of responses. This analysis will utilize the pre- and post-measures, but additional analyses will be conducted using generalized least squares regression (PROC MIXED in SAS ver 9.3 or higher) to account for missing data (drop outs between 6 weeks and 12 weeks).

Characteristics of dropouts and/or noncompliant individuals (those who do not walk and/or form any connections) will be intensively examined to shed light on potential weaknesses of the app (differential dropout overall or within certain subgroups). The evaluation of the app will include its impact using the pre-post data. As noted, examination of the correlation matrices along with the mean changes will inform whether the variables appear to move similarly in both groups. Thus, one might argue that it is not necessarily the best control choice since we would then be measuring the intensity of intervention. Alternatively, very different correlation structures will inform us about how the interventions are working and may provide information on appropriate controls and or strengths and weaknesses.

Utilization data will be examined to understand the acceptability and intensity of interactions with the apps. The penetration of the apps into this minority at-risk population is very important in potentially understanding, not only market share, but also potential impact. Complier average causal effect models²⁰³ will be used to examine the intensity of the intervention app’s utilization. Mediation models using the latest bootstrapping methods^{204,205} will be examined to enhance evidence that the changes induced by the treatment effects are consistent with the changes being mediated via the app and the intervention.

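### Stratification of randomisation by site is not specified and the Aim 3 analysis has no site term or by-site estimate, although the plan says that its two sites differ

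*Combined protocol and SAP*

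**What the plan says.** **Allocation.** Three places in the combined protocol and SAP describe it.
- Section 3C.1: "Participants will be recruited from Denver, CO and San Jose, CA and randomized individually to either the" test app or the comparison app.
- Section 3C.4: "Individuals will be randomized to one of two experimental conditions, using a customized computer program".
- Section 3C.6.1, after the baseline surveys: "participants will be randomized using the software and randomization allocation".

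None names a stratification factor, a block scheme or site. None says that allocation is unstratified either.

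**Numbers.** Section 3C.4 fixes "100 from the Denver area and 100 from the San Jose area". Sections 3C.6.3 and 3C.6.4 plan 100 women per arm.

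**Site differences.** Section 3C.5 gives two reasons for the second site: it tests the database protocol in a new location, and it "tests the app with a different demographic makeup of U.S. Latinas". Section 3C.3.1b says that a new location database will be built for San Jose by the Denver procedures. The app description just before Section 3C.3.1 says that the test app matches nearby registered users for walks.

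**Analysis.** For Aim 3, Section 3C.8 lists t-tests followed by "analysis of covariance to assess the outcome results adjusted for baseline (rather than change from baseline", then Hotelling's T² and PROC MIXED. No site term, site-by-arm term or by-site summary is listed. Region appears only under Aim 2, as "feasibility testing showing that location-based services can be replicated regardless of region". The only other covariate planned against bias is dropout status (Section 3C.6.5). Section 6 plans a check on the success of randomisation after data collection, with no stated consequence for site.

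**The concern.** Where sites are known to differ, site is normally a stratum in the allocation and a term in the model. Three things are at stake here.

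1. **Noise and chance imbalance in H1.** If mean change in physical activity differs between the cities and the arms hold different shares of each city, part of the site difference enters the arm difference.
2. **Intensity of the intervention.** The test-arm women in a city are each other's possible walking partners. An uneven split within a site changes the partner pool there. This is specific to an app that matches nearby users.
3. **Evidence from the second population.** San Jose was chosen partly because its Latinas differ from Denver's. Only the test app uses the location database, so site could modify the effect as well as the outcome level. No planned output shows the physical-activity effect in San Jose, so a pooled H1 result could come mainly from Denver, where the prototype was developed and field tested.

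The third point does not depend on any imbalance.

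**Working it through.** **Inputs from Section 3C.8:** difference 144.7 min/week; SDs 355.7 and 179.1; two-sided alpha 0.05; 90% power; 20% dropout. From Section 3C.4: 100 women per site.

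**Assumption:** the documents give no site difference, so a difference D in mean change of 25 to 150 min/week is used throughout. Its variance is treated as part of the plan's SD.

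**Step 1. The plan's own figures.** A Welch test (noncentral t, Satterthwaite df) needs 81 per arm for 90.03% power, as stated. The second scenario (178.0 − 71.5 = 106.5; SDs 234.9 and 179.1) needs 82, as stated. At 100 per arm with 20% dropout, 80 per arm complete.
- Root-mean-square SD = √((355.7² + 179.1²)/2) = 281.6.
- Standard error at 80 per arm = 281.6 × √(2/80) = 44.5 min/week.

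**Step 2. Site gap between arms if allocation is not stratified.** The gap is the share of Denver women in the test arm minus that in the comparison arm.
- With totals fixed at 100:100 and k Denver women in the test arm, the gap is (2k − 100)/100. The variance of k is 100 × 0.5 × 0.5 × 100/199 = 12.56, so its SD is 3.54 and the SD of the gap is 7.1 points.
- With simple allocation the exact binomial calculation also gives 7.1 points.

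| | Gap ≥ 10 points | Gap ≥ 20 points |
|---|---|---|
| 100 per site, simple | 0.18 | 0.006 |
| 100 per site, fixed 100:100 | 0.20 | 0.007 |
| 80 per site, simple | 0.24 | 0.014 |
| 80 per site, fixed 1:1 | 0.27 | 0.017 |

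The 80-per-site rows represent completers, with dropout taken as unrelated to arm and site.

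**Step 3. Partner pool.** An even split puts 50 test-arm women at each site. The 95% range is 40-60 under simple allocation and 43-57 with totals fixed at 100:100. The count falls outside 45-55 in 27% and 12% of trials respectively.

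**Step 4. Shift in H1 = gap × D.**
- 10-point gap: 0.10 × 25 = 2.5 to 0.10 × 150 = 15 min/week, or 2% to 10% of 144.7.
- 20-point gap: 5 to 30 min/week, or 3% to 21% of 144.7.

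Given the gap, two-sided type I error for D of 50 to 150 is 5.1% to 5.5% (10 points) and 5.5% to 9.4% (20 points). Averaged over randomisations it stays at 5%.

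**Step 5. Power from adding site.** With equal site sizes, site contributes D²/4 to the variance, so the adjusted SD is √(281.6² − D²/4). Power by normal approximation at 80 per arm is 90.2% without site.

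| D (min/week) | Site share of variance | Power with site |
|---|---|---|
| 25 | 0.2% | 90.2% |
| 50 | 0.8% | 90.4% |
| 100 | 3.2% | 91.0% |
| 150 | 7.1% | 92.1% |

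**Step 6. If the program already stratifies but the model omits site.** The test uses too large an SD. Actual alpha is 2 × (1 − Φ(1.96 × 281.6/adjusted SD)) = 4.9%, 4.6% and 4.2% for D = 50, 100 and 150.

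**Step 7. Precision of a by-site estimate.** With 40 completers per arm at a site, the standard error is √((355.7² + 179.1²)/40) = 63.0, and the 95% half-width is 1.96 × 63.0 ≈ 123 min/week.

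**The case against.** The strongest reply is that little is at risk. Women are randomised individually at both sites, so the estimate is unbiased over randomisations, and a gap large enough to matter is rare. The planned baseline adjustment would absorb part of any stable site difference in activity. Adding site raises power by at most about 2 points over the assumed range. A by-site interval of about ±123 around a planned effect of 144.7 settles nothing. All of this stands.

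Three stronger readings are tempting, and the documents do not support them.
- **Allocation is unstratified.** A reader might infer this, but it would be read from silence. The program's scheme is not described, and Figure 5 (study design) could not be read in the copy reviewed. The imbalance figures in Steps 2 to 4 are therefore conditional.
- **The company runs every Denver visit and the university every San Jose visit.** Section 5E says only that both institutions conduct the research. Section 3C.3.1d gives the San Jose focus groups to a separate team, but no section assigns the trial visits by site.
- **Confirming the effect in San Jose is a trial objective.** H1-H3 are pooled, and one of the two reasons for the second site is the database work under Aim 2.

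The reply does not dispose of the absence of any site term or by-site result for Aim 3, in a plan that itself names two target populations. The partner-pool argument is plausible from the app's design, but the documents give no figure linking pool size to walking.

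**Conclusion.** The point holds as a free improvement. Site appears neither in the described allocation nor in the Aim 3 analysis, although the plan says that the sites differ in population and in a database that only the test app uses.

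A reader might infer that arm and site are confounded. The documents do not support that: both sites contribute to both arms, unconditional type I error is 5%, and the sample size of 200 is unaffected. For the most likely imbalances the shift in H1 is well under one standard error: 2.5 to 15 against 44.5 min/week for a 10-point gap. That rests on unstratified allocation and on site differences of 25 to 150 min/week, neither of which the documents state. If allocation is already stratified, the cost is instead a slightly conservative test (alpha 4.2% to 4.9%).

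The larger gain is informational: a by-site estimate would give effectiveness evidence, however imprecise, in the population that partly motivated the second site.

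**What to change.** 1. In Section 3C.4, state the allocation scheme: 1:1 in permuted blocks of varying size, stratified by site. If the program already does this, say so.
2. In Section 3C.8, add site as a fixed covariate to the H1-H3 ANCOVA and PROC MIXED models.
3. Report the H1 arm difference separately for Denver and San Jose with 95% confidence intervals. Label these descriptive, give the expected half-width of about 123 min/week, and do not present them as a powered interaction test.

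The cost is one setting in the in-house randomisation program before enrolment and one degree of freedom in the models. No extra participants, visits or measurements are needed. Items 2 and 3 do not depend on how allocation was done, so they remain available even if the program can no longer be changed.

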Retention, Tracking, and Attrition: Although participants can withdraw at any time, steps will be used to minimize dropouts to ensure high internal validity. Participant progression will be tracked. Staff will use behavioral reinforcement strategies known to be effective in the behavior change literature¹⁹⁸⁻²⁰⁰ and be trained to develop rapport with participants by communicating expectations for participants and staff. Personalizing this relationship will enable participants to be more direct about problems, providing a strong foundation for problem-solving. While drop-out rates vary in community walking program for Latinos, we conservatively planned for 20% attrition.²⁰¹ Our Phase I attrition was 10%. We assume equal adherence across the two treatment groups, because we have no data to predict otherwise. Our method of tracking and multiple contacts will help us retain some of these participants for intent-to-treat purposes, despite their discontinued app use. Participants will provide contact information for two individuals who can always contact them and update contact information at each assessment. If they do not respond to email/text reminders, we will follow-up by phone. Finally, we will create a dummy coded variable for each respondent where 1=completers and 2= drop outs and test for associations with key variables in our analytic models. If bias is identified, we will control for it by adding it as a covariate.

Compensation: All participants (n=200) will be compensated to incentivize and improve study retention. A \$100 gift card will be given for completing all study assessments (baseline, 6-week, and 12-week).

App Use: Implementation of technology-based interventions can be challenging due to participants forgetting, fatiguing, or believing they have learned all they need to know. In order to bolster compliance with using either of the assigned app, weekly reminders to use the app will be sent to participants by text message.

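### Does the 3-month recall of the social-support survey spoil its week-6 comparison?

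*Combined protocol and SAP*

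**What the plan says.** Section 3C.6.2 describes the Social Support for Exercise Survey as a 13-item scale on how often friends or family "encouraged their exercise behaviors during the previous 3 month". Under the baseline heading of section 3C.6.1, randomisation takes place at the same visit: "After survey completion, participants will be randomized using the software and randomization allocation".

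Table 4 has a row for social and environmental support, marked at baseline, week 6 and week 12. The week-6 visit is described thus: "Participants will complete interim assessments of initial changes". It is completed online, with a reminder after 3 days and then "3 more reminders at 3-day intervals if still not completing it". Section 3C.6.5 adds: "If they do not respond to email/text reminders, we will follow-up by phone".

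In section 3C.8, H2 states that women given the app "will report greater increases in their social support for exercise compared to Latinas randomized to the comparison app at 12-weeks post-test". A separate list of additional secondary analyses will "evaluate immediate changes in the PA, social and environmental support, and QOL measures at 6 weeks" and will "assess mediators at 6-weeks for a mediational analysis on 12-week outcomes". The mediators are not named. No section shortens the recall period at week 6, mentions that it reaches back before randomisation, or says how a week-6 result on support is to be read.

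**The concern.** Six weeks after randomisation, a question about the last 3 months covers a good deal of time before the app was installed. Whatever weight a woman gives to those weeks dilutes the comparison, because the arms do not differ in expectation over that period. Adjusting for baseline does not restore the lost contrast.

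This looks awkward because social support is the mechanism through which the app is meant to work (section 3A.2). CHAMPS, the physical activity measure, looks back only 4 weeks. At day 42 its window opens on day 42 − 28 = 14, wholly after randomisation. The week-6 results could therefore show activity moving and support standing still, partly because the two questionnaires look back over different periods. A reader who missed this might conclude that the app does not act through support.

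**Working it through.** **Overlap.** Inputs are the 3-month recall (3C.6.2), read as L = 84, 90, 91 or 92 days; day 0 at the baseline visit (3C.6.1); week 6 as day 42; the first reminder on day 42 + 3 = 45 and the last on day 45 + 3 × 3 = 54; and week 12 as day 84. The share of the window before randomisation is (L − d)/L:

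| Day d | L = 84 | L = 90 | L = 91 | L = 92 |
|---|---|---|---|---|
| 42 | 42/84 = 50% | 48/90 = 53% | 49/91 = 54% | 50/92 = 54% |
| 54 | 30/84 = 36% | 36/90 = 40% | 37/91 = 41% | 38/92 = 41% |
| 84 | 0% | 6/90 = 7% | 7/91 = 8% | 8/92 = 9% |

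Completion later than day 54, after a phone call, lowers the share further. The plan gives no timing for those calls.

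**The plan's power figure.** Section 3C.8 powers physical activity only. A difference of 216.2 − 71.5 = 144.7 with SDs of 355.7 and 179.1 needs 81 per group for 90% power by the unequal-variance t-test, which reproduces the stated figure. For the support scale the plan gives no SD, effect or power, so everything below is illustration.

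**Dilution with the SD held fixed.** If w is the weight given to the weeks after randomisation, the expected contrast is w times the full contrast. With equal weighting, w = 42/91 = 0.46. Borrow the standardised activity effect, 144.7/√[(355.7² + 179.1²)/2] = 144.7/281.6 = 0.51, and take 100 × 0.8 = 80 completers per arm. Power is Φ(δ√(80/2) − 1.96). The full effect of 0.51 gives about 90%; the diluted effect, 0.51 × 0.46 = 0.24, gives about 32%.

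**Dilution with baseline adjustment.** The SD does not stay fixed. Let P and Q be support before and after randomisation, each with variance 1, correlation ρ and no measurement error. The baseline score is P and the week-6 score is wQ + (1 − w)P. Given P, the week-6 variance is w²(1 − ρ²), against 1 − ρ² for Q alone. Contrast and residual SD both shrink by the factor w, so their ratio is unchanged and power stays at 90%. Measurement error breaks this balance. With assumed reliability of 0.7-0.9 and assumed correlation of 0.3-0.7, ANCOVA power is 43-73% under equal weighting. It is 76-87% if recent weeks dominate so that w = 0.75.

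**Mediation.** In the same error-free model with baseline adjustment, the path from arm to week-6 support is multiplied by w and the path from support to outcome by 1/w. Since w × 1/w = 1, the indirect effect is unchanged. It shrinks only through measurement error, as above.

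**Would rewording help?** A 4-week window at week 6 would leave out the first 14 of 42 days on the app (33%), or 26 of 54 (48%) at the last reminder. If the shortened recall were 0.1 less reliable, power would be 84-86%. That is a clear gain over 43-73%, but little or none over 76-87%.

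**The case for a change.** The best case for acting is that the facts come from the plan itself, the direction of the effect follows from randomisation, and a few sentences would guard against misreading a null result on the app's central mechanism. The direction stands, and so does the figure of about half at the scheduled visit.

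The rest is weaker. Table 4 names no instruments, and the plan does not give the week-6 wording. Unmodified use is the likely reading, but it remains an inference. Nowhere does the plan say that a week-6 null will be taken as absence of effect, so the harm depends on a reading the authors have not proposed. A standing rule that a week-6 null may never count against the mechanism would be one-sided: if recent weeks dominate recall, the result is nearly as informative as it would be without overlap. Section 3C.8 already prefers analysis adjusted for baseline to change scores, though without naming a visit.

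Week-6 data may also enter the mixed model that 3C.8 plans for dropouts between the two follow-ups. If that model has a separate mean for each arm at each visit, a diluted week-6 difference need not bias the 12-week contrast.

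**Conclusion.** The overlap is real: 50-54% of the recall window at day 42 and 36-41% at the last reminder, assuming the 3-month wording is kept at week 6. It pulls the expected week-6 difference in support towards zero by an amount the documents cannot settle. The illustrative 32% to 90% power range reflects the choice of recall weights, reliability, correlation, analysis and a 90% starting point, none of which the plan supplies for this scale.

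No change follows. The effect is confined to an additional secondary analysis and, if support is chosen as a mediator, to the 6-week mediation model; no decision in the plan rests on either. H1 and H3 use other instruments. H2 is tested at 12 weeks, when the recall period and the time since randomisation almost coincide (0-9% overlap). The error can only hide a difference, not create one.

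Altering the recall period at one visit would give up the published wording and comparability across visits for a gain that may be nil. Sections 3C.6.2 and 3C.9 rely on validated scales, so keeping it is a defensible trade-off. What remains is a point of interpretation: a careful analyst would mention the overlap, show the baseline-adjusted week-6 estimate with its confidence interval, and rest the conclusion on H2.
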